10.1. Covariate Adjustment

Consistent with usual practice, we will only adjust the primary analysis for stratified variables (age (</>70; sex and low-income status) (48).

Assuming that randomization has worked, and we have approximately equal distribution of sociodemographic and clinic characteristics between randomization groups, we will not adjust our analyses for covariates, as this should have been dealt with through the process of randomization. If there is imbalance in important covariates between randomization groups, a sensitivity analysis will be conducted statistically adjusting for these imbalanced covariates through the modelling process.

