10.8. Planned Subgroup Analyses

We have a priori specified particular subgroup analyses, considering the biological plausibility for subgroups. We will conduct analyses stratified by subgroup, as described in the primary and secondary outcomes sections. We will provide effects with confidence intervals for subgroups (rather than p-values), as tests of interactions for subgroups can fail to detect important effects. These will be presented in a forest plot (49,50).

The subgroups of interest include:

Gender: Men vs Women (self-reported), likely exclude gender diverse

Age: >70 years vs 65-69 years

Income group: <30,000 vs >30,000

Financial barriers: Present vs Absent

Condition type: Diabetes // CKD // ASCVD // Risk factors only

Multimorbidity: 1-2 vs 3-4 indicated conditions

Primary Care Relational Continuity: Low/Medium vs High

Specialist Involvement in the year prior to randomization: Yes vs No

On statin at baseline: Yes vs No

On ACE/ARB at baseline: Yes vs No

Living environment: supported living vs. Independent living

Baseline medication adherence: >80% PDC for all covered meds vs <80% for any covered med

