10.9. Sensitivity Analyses

Sensitivity analyses will be conducted as follows:

- Excluding those who have admissions/costs in the top 1% of all participants
- Excluding participants who resided in the same household as another participant.
- We will also conduct a complete case analysis to examine the effects of the missing data, where relevant (ie. Self-reported outcomes).

11. Interaction between intervention arms

Given the factorial design of the trial, we will assess for multiplicative interaction. Because each of our two interventions was designed to address very different patient barriers to

medication adherence (financial barriers vs. Knowledge/motivation), we don't anticipate major multiplicative interaction effects.

12. Health Economic Analysis

The primary outcome will be mean total 3-year in-study health care costs for patients receiving copayment elimination (or not) and those receiving MOXIE (or not), adjusting for co-intervention received. We will include costs for hospitalization and ED visits, physician claims (specialist and primary care physician visit and procedure billing costs), prescription medications (including those subject and not subject to copayment elimination), nonphysician ambulatory costs (day medicine and day surgery clinics), and outpatient diagnostic imaging and laboratory costs. The total costs will be calculated as the sum of these costs. Alberta Health uses Canadian Institute of Health Information case-mix grouper methods to estimate hospital costs and ambulatory-case costing methods to estimate outpatient costs.

Physician claims will be based on the amount paid by Alberta Health. The cost of medications will be estimated by combining a database containing a comprehensive list of medications dispensed to all Alberta residents with a price list from Alberta Blue Cross, including dispensing fee. Diagnostic imaging and laboratory costs will be based on estimates provided by Alberta Health Services. All costs will be reported in 2021 Canadian dollars.

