Assuming a non-gaussian distribution of costs, we will use established methods to enable comparisons of mean total costs, as these are easily interpretable and relevant to health care payer. We will use non-parametric bootstrap estimates to derive standard deviations and 95% confidence interval (95% CI) and mean cost differences between the treatment arms as we have done. We will use 1000 bias-corrected bootstrap replications, and sample with replacement from the original data, we will estimate the distribution of a sampling statistic to derive 95% confidence intervals. To allow us to control for stratified variables (age ≤ 70 ; sex and low-income status), we will also use generalized linear models to compare total costs across groups, using a gamma distribution and log-link function.

13. Statistical Software

We will conduct all the analyses using SAS software, version 9.4 (SAS Institute Inc, Cary, North Carolina), and Stata, version 17 (Stata Corp, College Station, Texas).

14. Differences to the protocol

None

15. References

1. Mirolla M. THE COST OF CHRONIC DISEASE in CANADA EXECUTIVE SUMMARY. 2004;

7. Mortality, Summary List of Causes. 2008; Available from: www.statcan.gc.ca,
8. Health Agency of Canada P. Leading Causes Of Hospitalization, Canada, 2009/10; Available from: www.publichealth.gc.ca

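### The planned cost comparison adjusts for no baseline variable in its bootstrap and uses pre-randomization cost nowhere, so its interval is probably wider than it needs to be

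*Combined protocol and SAP*

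**What the plan says.** Health care cost is a secondary outcome (combined protocol and SAP, section 4.4). Section 12 makes average cost per participant over three years the endpoint of the economic analysis, for each intervention against its absence, "adjusting for co-intervention received". The method follows in the same section: "We will use non-parametric bootstrap estimates to derive standard deviations and 95% confidence interval (95% CI) and mean cost differences between the treatment arms". The interval is specified further as "We will use 1000 bias-corrected bootstrap replications". This bootstrap text names no covariate.

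A second analysis brings in the strata. "To allow us to control for stratified variables" (age group, sex and low-income status), the plan says "we will also use generalized linear models to compare total costs across groups, using a gamma distribution and log-link function". It does not say whether that model will be reported as a cost ratio or as a mean difference.

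Three other places bear on the point:
- Section 10.1 sets the general rule: "we will only adjust the primary analysis for stratified variables". Other covariates come in only through a sensitivity analysis, and only if an imbalance is observed.
- Sections 10.2 and 10.9 respond to very heavy users by excluding the top 1% of encounters or costs.
- Section 10.8 already looks back before randomization, with a subgroup defined as "Specialist Involvement in the year prior to randomization: Yes vs No" and another by baseline medication adherence. Section 8 describes linkage by health number to claims, hospital, ambulatory, pharmacy and laboratory data.

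**The concern.** Total cost is typically very skewed, and a small number of heavy users can carry much of its variance. Section 10.2 recognizes this and worries that an uneven split of such participants could distort the comparison. Some heavy users can be predicted from their use before randomization. Prior cost is the natural baseline value of this outcome, yet no cost analysis contains it.

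The two planned safeguards do not fill the gap. The section 10.1 sensitivity analysis depends on an imbalance being noticed, does not name prior cost, and does not aim at precision. The top-1% exclusion selects on something measured after randomization that the interventions may affect, and it no longer estimates mean cost in everyone randomized.

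What is at stake is the width of the interval. The SAP's introduction reports that copayment elimination did not lower health care costs. With a finding of that kind, the interval tells a payer which savings or increases can be ruled out.

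**Working it through.** **The plan's own figure.** No standard deviation, target difference, power or interval width is given for cost. The only precision figure is the sample size for the clinical outcome (section 4.8). It reproduces with the Poisson-regression formula for a binary exposure split 1:1, with rate 0.14 per year, 3 years, rate ratio 0.88, 80% power and two-sided alpha 0.05 (sidedness assumed):

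N = [1.960 × √4 + 0.8416 × √(2 + 2/0.88)]² / [(ln 0.88)² × 0.14 × 3] = 4667, and 4667 × 1.01 = 4714.

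This matches the plan, but it concerns event rates and says nothing about cost precision.

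**Inputs for the cost comparison.** Number randomized: 4768 (section 7.1), about 2384 on each side of each intervention. Within-arm correlation r between pre-randomization cost and three-year cost: not in the documents, so assumed over a range.

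**Formulas.** Linear adjustment for a baseline variable multiplies the standard error, and so the interval width, by √(1 − r²). The unadjusted trial giving the same precision would need 4768 / (1 − r²) participants.

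| assumed r | width factor | interval narrower by | equivalent unadjusted N |
|---|---|---|---|
| 0.2 | 0.980 | 2% | 4967 |
| 0.3 | 0.954 | 5% | 5240 |
| 0.4 | 0.917 | 8% | 5676 |
| 0.5 | 0.866 | 13% | 6357 |
| 0.6 | 0.800 | 20% | 7450 |

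**Check with skewed costs.** The formula was tested by simulation: lognormal costs with log-scale SD 1.2 (assumed), 4768 participants, no effect of either intervention, 2000 runs. Raw-scale correlations of 0.17, 0.33 and 0.55 gave standard-error ratios of 0.985, 0.945 and 0.848. The formula predicts 0.985, 0.943 and 0.838.

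**Does adjusting for the other intervention do the same job?** In the same simulation it gave a ratio of 1.000. A factor split evenly that shifts cost by d standard deviations explains only d²/4 of the variance, so it helps little unless its own effect on cost is very large.

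**The case against.** The strongest reply has five parts.

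1. *The comparison is not wholly unadjusted.* Correct: section 12 adjusts for the co-intervention and adds a model with the strata. But the co-intervention is not a baseline variable and brings no precision, and the strata do not reach the bootstrapped difference.

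2. *The plan already has a remedy for imbalance.* Correct: a reader might infer that the top-1% exclusion is the only one, but section 10.1 provides another. It is conditional and secondary, so the precision point remains.

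3. *The size is unknown.* This stands. Nothing in the documents fixes r, and one prior year has to predict a three-year total. At r = 0.1 the factor is √(1 − 0.01) = 0.995, a trivial gain. Section 4.8's 80% power belongs to the clinical outcome, so no power statement for cost can be drawn from the plan.

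4. *The gamma model can yield a mean difference.* It can. A reader might infer from the log link that only a ratio will be reported, but the documents leave the scale open. The gap is in specification and is not an error.

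5. *The data may not be there, and the result is out.* Section 10.8 shows a yes/no for specialist involvement in the prior year. It does not show prior admission or visit counts, and linkage does not prove that a costed look-back year was extracted. A new headline estimator chosen now would be post hoc. Both limits stand and shape the fix.

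**Conclusion.** The point holds as a modest improvement in efficiency on a secondary outcome. The mean cost difference and its interval come from a bootstrap with no baseline covariate, and pre-randomization cost or use enters neither cost analysis.

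A reader might go further and infer that the cost comparison is biased, or that chance imbalance makes its interval unreliable. The documents do not support that. With 4768 randomized, the bootstrapped difference is valid under randomization and its interval already allows for chance imbalance.

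The gain rests on the assumed r and on a roughly linear relation between prior and in-trial cost. It is negligible near r = 0.2 and becomes material at about 0.5, where the interval would be 13% narrower. At this sample size, adding a few covariates costs essentially no precision even if r proves small, and the estimand is unchanged.

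**What to change.** In section 12, specify a covariate-adjusted mean difference:

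- Within each of the 1000 bootstrap replicates, regress total cost on both intervention indicators, the three stratification factors and cost in the 12 months before randomization. Report the adjusted marginal mean difference with the bias-corrected interval.
- If costs for that year are not in the extract, use pre-randomization utilization derived from the linked databases. The prior-year specialist indicator in section 10.8 is one such variable, though a yes/no term will probably recover less.
- Put the same baseline term in the gamma model and state its scale: average each participant's predicted cost with the intervention set on and then off, and report the difference.
- Keep the unadjusted bootstrap as a supporting analysis.

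The stratification part needs no new data. The rest costs the extraction and costing of one look-back year, plus a rule for participants whose look-back is incomplete. Because the copayment cost finding is already reported, a re-analysis of this trial should be labelled supplementary and should not replace the planned estimate.
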